5.4 Statistical Methods

Analyses will be conducted at the level of individual patient data using generalized linear mixed effects regression with a random effect to account for clustering by EMS service, and fixed effects for treatment and time interval to account for the stepped wedge design. The primary and co-primary outcomes will be analyzed using binomial distribution with identity link and the effect of intervention will be expressed as absolute differences with 97.5% confidence intervals. Secondary outcomes will be similarly analyzed using binomial distribution and identity or logit link for dichotomous variables, normal distribution and identity link after log-transformation or gamma distribution and log-link for continuous variables with a skewed distribution, or Poisson or negative binomial distribution with log link for count variables. The effect of the intervention on each secondary outcome will be described using absolute difference, Relative Risk or Odds Ratio with 95% confidence interval. Subgroup analyses (described below) will be conducted by including interactions with time interval and treatment in the regression model.

Our **health economist** will perform a cost-effectiveness analysis from the perspective of the Ministry of Health and Long-Term Care. Trial data will be used to populate the relative costs and outcomes of the use of the CCR by paramedics with usual care (100% immobilization). Resource use will be collected during the trial and obtained from ICES, while unit costs will be obtained from appropriate Canadian

sources, such as Schedule of Benefits for Physician Services. Total cost for each patient includes costs of the intervention and costs of health services, including the follow-up period of 30-days post ED discharge. Cost of intervention covers cost of training and operation. Costs of operating paramedic services include personnel cost (e.g. salaries and employee benefits), service cost (e.g. fuel, maintenance), medical supplies (e.g. an on-board liquid oxygen system, medications, and single-use patient care supplies). Costs of healthcare services will be obtained from ICES and will be estimated by multiplying the unit costs by the volume of healthcare used. We will use mixed-effects regression analyses to estimate the difference in expected healthcare costs and outcomes between the intervention and control groups. The incremental cost-effectiveness ratio will be estimated by dividing a difference in cost by a difference in the number of immobilizations. The 95% confidence interval will be calculated using a non-parametric bootstrapping method. Results from the bootstrapping exercise will also be used to depict a cost-effectiveness acceptability curve (CEAC), which links the probability of a treatment being cost-effective to a range of potential threshold values (λ) that the health system may be willing to pay for an additional unit of effect (17). A CEAC is a graphical representation of the probability that the CCR may be cost effective given alternate dollar values placed on an outcome. This will allow estimation of the probability that the CCR can be considered cost-effective given the available data. In addition, sensitivity analysis will be undertaken to examine the effect of conducting a complete caseonly analysis and of varying the cost of the intervention.

We will also conduct a budget impact analysis to estimate the financial consequences of implementing the CCR by paramedics in Ontario. All analyses will be conducted using STATA version 13.0 and Microsoft Excel and Visual Basic for Applications.

Pre-Specified Sub-Group Analyses will be conducted to examine the differential effects (possible inequity) of the intervention on the following groups, defined by:

- a) sex
- b) language barrier present vs. not (collected by paramedics on data collection form),
- c) long transport times (longer vs. shorter than 15 min),
- d) age (adult ≥16 vs. children <16),
- e) socioeconomic status and education level (ICES data), and
- f) type of backboard used (full board, open-back scoop, or trunk and neck KED devices).

Section 6. Methods: Monitoring

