Primary outcome(s)	Proportion of patients immobilized Proportion of patients feeling comfortable (co-primary outcome)
Key secondary outcomes	Proportion of patients with a pain score ≤ 4/10 Time from EMS arrival to ED discharge or admission to hospital Patient radiation exposure from diagnostic imaging Number of skin pressure injuries Number of missed c-spine injuries Time spent in the field by paramedics before arrival to hospital Time spend in-hospital by paramedics before transfer of care

ED length of stay

Number of subsequent ED visits within 30 days

Number of subsequent clinical/family physician visits within 30 days

Frequency of c-spine diagnostic imaging performed within 30 days

Incremental cost per one immobilization avoided

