2.1 Background

Problem: Ontario Emergency Medical Services (EMS) annually transport half a million patients with a potential neck (cervical/c-spine) injury, from falls or motor vehicle collisions, to local emergency departments (ED). Ninety-five percent of those patients are alert and stable and at low risk of c-spine injury. Less than 1% actually have a c-spine fracture, and even less (0.5%) have a spinal cord injury. Spinal cord injuries result from moderate to severe blunt traumas and not from minor movements occurring during transport to hospital. Regardless, current EMS practice is to transport all such trauma victims (with or without c-spine injury) by ambulance using backboards, collars, and head immobilizers. These patients stay fully immobilized until an ED bed is made available, sometimes for as long as 3 hours. This prolonged immobilization is often unnecessary and increases patient discomfort, contributes to ED crowding, prolongs EMS intervention times, and adds a heavy financial burden to our healthcare system.

Why C-Spine Immobilization of Low-Risk Patients May Be Unwarranted: Not only is immobilization often unnecessary, its potential for clinical adverse effects and discomfort are well documented (3). Chest straps used in immobilization can have a pulmonary restrictive effect, even in healthy non-smokers. Immobilization on a board leads to progressively worse pain in the head, neck, and back area, often resulting in the necessity to perform diagnostic imaging on an otherwise normal spine in the ED. The presence of a c-spine immobilization collar has been associated with hyperextension, actually causing spinal cord injury in patients suffering from ankylosing spondylitis. In addition, c-spine collars can cause neck vein compression and increased intra-cranial pressure for patients with head injury, difficulty swallowing, and local skin necrosis.

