Once on an ED stretcher, it is not unusual for these patients to remain fully immobilized for several hours until physician assessment and c-spine diagnostic imaging can be performed and interpreted. This consumes valuable time for physicians, nurses, and radiology technicians and distracts them from other urgent responsibilities. These delays compound the burden of our crowded Canadian EDs in an era when they are under unprecedented pressures. The median length of stay for a patient evaluated in the stretcher area is approximately 8-12 hours, whereas similar minor trauma victims arriving without immobilization can be evaluated and discharged in less than 4 hours.

The Canadian C-Spine Rule: We have derived, validated, and implemented the Canadian C-Spine Rule (CCR) to be used by physicians (7-9), triage nurses (10), and paramedics (11) in more than 40,000 alert and stable trauma patients. The CCR (Figure 1) directs that immobilization is unnecessary if the patient has no high-risk criteria, has at least one low-risk criterion, and can voluntarily rotate their neck 45' left and right. Physicians and nurses already use the CCR in the ED to safely remove immobilization devices without the need for imaging and with no documented adverse outcomes. We recently completed a pilot implementation study with Ottawa paramedics where selective patients were transported without immobilization. We have recruited 3,854 patients, and paramedics have identified all clinically significant injuries (100% sensitivity) without negative consequence when the CCR determined that immobilization was not required (68% specificity). Approximately 60% of immobilizations were avoided.

[figure not shown]
C-Spine Evaluation in Children: The NEXUS decision instrument for use in adults and children was validated in 2,160 children aged 8 to 17 (12) and identified all significant injuries. The CCR's performance was superior to that of the NEXUS decision instrument when prospectively compared in an adult population (13), but has yet to be implemented for use in children. A case-control study of children younger than 16 with c-spine injuries identified 8 risk factors for significant injuries, 7 of which are included in the CCR (14).

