3.4.2 Measures of Patient Benefit

- a) Proportion of patients feeling comfortable (score ≤4 on a 10-point Likert scale) (co-primary outcome of interest),
- b) Proportion of patients with a pain score ≤4 on a 10-point Likert scale upon arrival at the Emergency Department (ED),
- c) Time from EMS arrival to ED discharge or admission to hospital,
- d) Patient radiation exposure (in millisieverts) from diagnostic imaging of the spine,
- e) Number of skin pressure injuries, and
- f) Number of missed clinically important c-spine injuries. A clinically important c-spine injury includes any injury other than the following defined unimportant injuries which require neither specialized treatment nor follow-up: isolated avulsion fracture of osteophyte, isolated fracture of transverse process not involving the body or facet joint, isolated fracture of the spinous process not involving the lamina, isolated simple compression fracture <25% of body height.

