6.2 Data Monitoring - Interim Analyses

The intervention period for this multi-centre study is fairly short - only 12 months long. Because of this, there are no interim analyses planned.

The number of c-spine injuries in eligible patients will be monitored as outcome information is available. We plan to obtain preliminary information on a small subset of study outcomes for safety assurance purposes before the first cluster of centres begin actively using the CCR. We will send the required information to ICES based on the first two months of enrollment following training (see Figure 2). Analysts at ICES will link our data at that time with the information available from the Ontario Health Insurance Plan (OHIP) database, as well as the Canadian Institute for Health — Discharge Abstract Database (CIHI-DAD). This will give us information on which cases had c-spine imaging performed, and of those, whether any c-spine injuries were identified. We will then review these cases to ensure that the CCR was applied appropriately and that no injuries were missed by either the paramedics, or the CCR itself.

The only situation that would trigger an immediate review to consider stopping the trial would be a situation where a spinal cord injury was sustained by an enrolled patient and believed to be a direct consequence of having transported a patient without immobilization resulting from the use of the CCR. In this case, we would notify the DSMB to review the available information and discuss their review and recommendations with the Steering Committee.

We would not consider a missed significant injury sufficient to warrant stopping the study as long as there was no consequence to the patient's safety and health i.e. not resulting in a spinal cord injury that was not already present before transport to the hospital. Any missed significant injury will be reported to both the DSMB and Research Ethics Board in a timely manner.

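### Radiation exposure is 0 mSv for patients who are not imaged, and neither model listed for skewed outcomes can include zeros; section 5.4 needs a rule for them

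*Combined protocol and SAP*

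**What the plan says.** Section 3.4.2, item d, lists "Patient radiation exposure (in millisieverts) from diagnostic imaging of the spine" as a measure of patient benefit. Table 1 in section 1.2 registers it as "Patient radiation exposure from diagnostic imaging". Neither entry limits the outcome to patients who had imaging.

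Section 5.4 analyses patient-level data with "generalized linear mixed effects regression with a random effect to account for clustering by EMS service", plus fixed effects for treatment and time interval. Skewed continuous secondary outcomes are given two options: "normal distribution and identity link after log-transformation or gamma distribution and log-link for continuous variables with a skewed distribution". On reporting, it says: "The effect of the intervention on each secondary outcome will be described using absolute difference, Relative Risk or Odds Ratio with 95% confidence interval". Section 5.4 does not name radiation. Nowhere do the documents mention zero doses, an added constant, a two-part or Tweedie model, or a quasi-likelihood fit.

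Two places show that some patients will not be imaged. Section 6.2 says of the ICES linkage: "This will give us information on which cases had c-spine imaging performed". Section 2.1 says: "Physicians and nurses already use the CCR in the ED to safely remove immobilization devices without the need for imaging". Section 2.1 also describes pain from immobilization on a board as "often resulting in the necessity to perform diagnostic imaging on an otherwise normal spine in the ED".

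**The concern.** Per-patient dose has a block of exact zeros (no imaging) and positive values for everyone else. The models in 5.4 suit the elapsed-time outcomes in 3.4.2 and 3.4.3 but not this mixture. A programmer who follows the text has two obvious ways to make the model run.

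- **Leave out the zeros.** The comparison becomes dose among imaged patients. Who is imaged is decided after the intervention and may be affected by it, so the randomized comparison is lost. Any benefit that comes from not imaging a patient is also removed.
- **Add a constant before taking logs.** The estimate then depends on the constant.

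At stake is whether this outcome can show a reduction in exposure that comes from avoided imaging. That is the route suggested by the background in section 2.1, although the plan does not tie that passage to this outcome or state an expected reduction.

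**Working it through.** The plan states no figure for radiation, so there is none to reproduce.

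**1. The models at zero.** The log of 0 is undefined, and the log-normal log-density at 0 is minus infinity. The gamma log-density at 0 is minus infinity for shapes 2 and 5 and plus infinity for shape 0.5. A zero therefore contributes no usable likelihood under either option.

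**2. How many zeros.** Section 3.6 gives 12 services × 4 intervals × 150 = 7,200 patients. Under Figure 2 the intervention cells number 4 × (3 + 2 + 1) = 24 of 48, so half the patients fall in each condition. Let p0 and p1 be the proportions imaged under usual care and under the Canadian C-Spine Rule. Zeros = 7,200 × [1 − (p0 + p1)/2]. The documents give neither proportion. Assuming p0 = 50%:
- p1 = 48%: 7,200 × 0.510 = 3,672
- p1 = 45%: 7,200 × 0.525 = 3,780
- p1 = 30%: 7,200 × 0.600 = 4,320

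**3. What each analysis estimates.** Let m0 and m1 be mean dose among imaged patients. Mean dose per patient is p × m, so the true ratio is (p1 × m1)/(p0 × m0). An analysis of positive doses estimates m1/m0 only. With m1 = m0:

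| Imaging, usual care to rule | True ratio | Positives only |
|---|---|---|
| 50% to 48% | 0.48/0.50 = 0.96 | 1.00 |
| 50% to 45% | 0.45/0.50 = 0.90 | 1.00 |
| 50% to 30% | 0.30/0.50 = 0.60 | 1.00 |

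**4. Check in the trial's own layout.** Simulation with 12 services, 4 intervals and 150 patients per cell. Assumed: log-normal dose if imaged, median 2 mSv, log-SD 0.7, between-service SD 0.2. There were 40 replicates, with service fitted as a fixed effect for simplicity. The last column is a log-link quasi-likelihood fit that keeps zeros.

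| Imaging | True | Log-normal, positives | Gamma, positives | Zeros kept |
|---|---|---|---|---|
| 80% to 60% | 0.75 | 1.008 | 1.011 | 0.763 |
| 60% to 40% | 0.667 | 0.996 | 0.992 | 0.652 |
| 60% to 24% | 0.40 | 1.004 | 1.001 | 0.388 |
| 40% to 30% | 0.75 | 1.022 | 1.023 | 0.769 |
| 30% to 12% | 0.40 | 1.023 | 1.026 | 0.410 |

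Positive-only fits stay near 1 whatever the true ratio; the fit that keeps zeros follows it.

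**5. Adding a constant k.** If dose among the imaged does not change, the ratio from log(dose + k) is exp{(p1 − p0) × (E[log(D + k)] − log k)}, where D is dose if imaged. A separate simulation (50% to 30%, assumed median 3 mSv, log-SD 0.7) gave 0.203, 0.320, 0.504 and 0.752 for k = 0.001, 0.01, 0.1 and 1 mSv, against a true 0.60. The log ratio is proportional to the fall in imaging. For 50% to 48%, one tenth of that fall, k = 0.001 gives 0.203^0.1 = 0.85 and k = 1 gives 0.752^0.1 = 0.97, against a true 0.96.

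**The case against.** Section 5.4 lists model families by type of variable for many secondary outcomes. It does not say that these are the only models permitted, that unimaged patients will be left out, or that a constant will be added. A reader might infer that the plan intends to analyse imaged patients only. The documents do not support that: the exclusion follows only if the listed models are applied literally to this outcome. A quasi-likelihood fit with a gamma-type variance could keep the zeros, but the plan does not specify one. The gap in the rule therefore stands, while any claim about the sponsor's intention does not.

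Avoided imaging also has its own outcome. Section 3.4.3, item f, counts c-spine imaging, and section 5.1 obtains imaging data through ICES, so a fall in imaging would probably be visible somewhere in the report. This lessens the harm without removing it. A frequency is not a dose, item f covers the cervical spine whereas 3.4.2 item d covers the spine, and item f counts 30 days from ED discharge whereas 5.1 counts 30 days from injury. Read literally, item f may miss imaging at the index visit.

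Finally, every rate and dose above is assumed. Since section 2.1 says ED staff already clear some patients without imaging, the real change could be small. That is fair, and it is why the 50% to 48% and 50% to 45% cases are shown.

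**Conclusion.** The concern holds in conditional form: the part of the effect due to avoided imaging would be missing from the radiation result unless zero handling is specified. This is more than missing detail, because the stated options either fail for this outcome or describe a subgroup formed after the intervention.

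The size depends on imaging rates that the documents do not give. With equal dose if imaged, positive-only analysis returns about 1.00 where the truth is 0.96, 0.90 or 0.60 for falls from 50% to 48%, 45% or 30%.

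A reader might go further and conclude that the trial would report an increase in radiation while mean dose falls. This requires imaged patients to receive more dose under the rule. For example, with 10% more dose and a fall from 50% to 30%, the true ratio is 0.60 × 1.10 = 0.66 and the positive-only ratio is 1.10. Nothing in the documents indicates such a rise, so this is a possibility and not a prediction. Nor do the documents establish that dose will fall substantially. The outcome is secondary, and the co-primary conclusions do not depend on it.

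**What to change.** Add to section 5.4 a rule for radiation exposure:

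- Analyse mean mSv per enrolled patient, with 0 for a patient who was not imaged. State the body region and time window that define this, and treat a patient who could not be linked as missing, not as zero.
- Fit a two-part model: binomial for any imaging, and gamma with log link for dose if imaged. Both families are already named in 5.4. Keep the same service, interval and treatment terms in each part.
- Recombine the parts. For each condition, average the product of predicted probability of imaging and predicted dose if imaged over all enrolled patients, and over the service effects. Report the absolute difference in mean mSv per patient, which is already a listed effect measure, with a 95% confidence interval from a bootstrap that resamples whole services or from the delta method.
- Do not restrict the analysis to imaged patients, and do not add a constant.

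Separately, reconcile the imaging window between 3.4.3 item f and 5.1.

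The cost is a short paragraph, slightly more complex code and an interval calculation that is approximate with 12 services. It needs no data collection beyond what the outcome already requires. Whether the software named in 5.4 fits both parts directly was not checked.

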3.3 Interventions

Paramedics will be trained in the use of the CCR prior to the start of the trial. We have conducted an Ottawa EMS CCR implementation pilot study and have designed our training program to address barriers identified in the pilot. The training entails one hour of education: 30 minutes of self-review of a teaching video addressing the background and scientific development of the CCR, and a 30-minute inclass teaching video reviewing the specific steps involved in using the CCR, complete with a demonstration and question and answer period with a certified trainer. Paramedics will be "certified" to clear the cervical spine by medical directive if they have: a) successfully completed the initial training sessions, and b) successfully completed (score of ≥80%) a written quiz. Paramedics failing the written quiz would be required to attend a remedial session and review all wrong answers with their certified trainer. Of note, Ottawa paramedics all successfully completed their training.

The stepped wedge trial will begin after paramedic training has been completed (see Figure 2). During the Usual Care phase, paramedics will complete the CCR data collection form for all eligible patients, but will continue to immobilize them all before transport to the receiving hospital. Once a community has crossed to the intervention CCR phase, paramedics will be permitted by medical directive to implement the CCR. Paramedics will then transport selected patients without immobilization according to the CCR. Although following the medical directive will be mandatory for paramedics, they will be encouraged and allowed to immobilize patients if they are uncomfortable with the CCR's recommendation to not immobilize them.

During the study set-up time period (Figure 2), each participating service will designate a local paramedic study champion. These individuals will be in close contact with staff at the Study Coordinating Centre and will receive further information about the study, the methodology and the implementation of the CCR. These individuals will be heavily involved in delivering the study training material at their particular location and will serve as a first point of contact throughout the implementation. Paramedics with questions about specific aspects of the CCR, or the application of the CCR for unusual scenarios will be able to communicate directly with a peer in an effort to promote adherence to the protocol.

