3.4.1 Measures of Patient and Health System Benefit

a) proportion of patients transported with immobilization (primary outcome of interest)

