
Appendix 7. Study Data Collection Form

Multicentre Eval				le by Paramedics
(To be com			ction Form ff at the Study Coordina	ating Centre)
SUBJECT #:	pieted by desi	gnateu Sta	ii at the study Coordina	aung Centre)
Paramedic Run Number:			Event date (yyyy/mm/d	ld):/_/_
Service:			Study Phase (Usual/Co	
Age (years): Unk	nown		Gender: ☐ Male ☐ Fe	
Transported: No Ves	□ Unknown			
 According to the "Ca 	anadian C-Spir	ne Rule" w	ould this patient require	e c-spine immobilization?
□No □Yes □In	determinate			
 Was this patient trans 	sported with o	-spine imr	nobilization?	
□No □Yes □Un	able to determ	ine		
 If yes, please check 				_
□ C-Collar □ Full I			KED ☐ Other (Specify	n:
		n of Injury	check all that apply):	
☐ Motor vehicle collision (if ye	s, see below)		☐ Fall onto head (ax	
☐ Motorcycle crash ☐ Other motorized vehicles			☐ Contact sports (ax	
☐ Pedestrian struck & thrown			☐ Heavy object onto ☐ Other Sports	neau (axiai loau)
☐ Pedestrian struck			☐ Bicycle struck	
☐ Fall from standing			☐ Bicycle collision	
□ Fall from sitting			☐ Other bicycle	
☐ Fall from elevation >10ft/15	stairs		☐ Assault blunt obje	ct
□ Fall from elevation ≥ 3-10ft/			☐ Assault fist or feet	
☐ Fall from elevation < 3ft/5 s			☐ Head struck by ott	ner object
□ Diving			☐ Hit head on an obj	ject
			☐ Other (specify):	 
If "MVC", speed? ☐ Stopped ☐ City speed (<60 km/hr) □ H	lighway sp	eed (60-100 km/hr) □ Hig	gh speed (>100 km/hr)
☐ Unknown speed Ejection from vehicle?	□ No	□Yes	□ Unknown	
Rollover?	□ No	□Yes		
Seatbelt use?	□ No	□Yes		
"Head-on" collision?	□ No	□Yes	□ Unknown	
Simple rearend?	□ No	□Yes	□ Unknown	
If "bicycle", helmet use?	□ No	□Yes	□ Unknown	
		Tim	es	
Arrive to Patient (HH:MM): _				
			Field Time (DS-AP)	(MM):
Depart Scene (HH:MM):			T	Del (MA)
Arrive Destination (HH:MM):			rransport rime (AL	D-DS) (MM):
ATTIVE DESURATION (FIR.MM):			Hospital Time (TC-	AD) (MM):
Transfer Care (HH:MM):			mospital raine (10	
 			Comfort	
Pain Medication Administer If yes:				
Туре	ose		Route	Frequency
				_
 				
Completed by:				
Date Initiated (yyyy/mm/dd): _				
Date completed (yyyy/mm/dd)				
-				
Data collection form, Version 1, Febru	ary 2016			
Date Collection forth, version 1, Febru	my 2010			

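### Subgroup (f), type of backboard used, is defined only for immobilized patients, so its treatment interaction cannot show whether the effect of the intervention differs by device

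*Combined protocol and SAP*

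**What the plan says.** Section 5.4 sets out subgroup analyses to "examine the differential effects (possible inequity) of the intervention on the following groups", and item (f) in that list is "type of backboard used (full board, open-back scoop, or trunk and neck KED devices". The method is given in the same section: "Subgroup analyses (described below) will be conducted by including interactions with time interval and treatment in the regression model".

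Appendix 7 shows how the device is captured. Study staff first record whether the patient was transported with c-spine immobilization. The device boxes come under a conditional follow-up, "If yes, please check". The parent item is the primary outcome in Section 3.4.1: "proportion of patients transported with immobilization (primary outcome of interest".

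Section 3.3 makes immobilization depend on phase. In Usual Care, paramedics complete the form "but will continue to immobilize them all before transport to the receiving hospital". After crossover, "Paramedics will then transport selected patients without immobilization according to the CCR", and where the rule advises against immobilization "they will be encouraged and allowed to immobilize patients if they are uncomfortable" with that advice. Appendix 6 has a box for this override.

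Nothing in the protocol defines a device for a patient who was not immobilized, defines it at service level or before assignment, or limits (f) to particular outcomes.

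**The concern.** A subgroup used to study effect modification should be fixed before, or be unaffected by, the intervention. Here it is a by-product of the primary outcome: a patient has a device level only if the outcome is yes, and the intervention determines who that is.

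Patients spared immobilization are the ones in whom the intervention acts, and they belong to no device level. Their benefit is therefore missing from each within-device contrast and from the differences between devices. The analysis is framed as a check on possible inequity, so a null interaction could be read as evidence that the benefit is the same whichever device is in use. The analysis could not have shown otherwise.

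**Working it through.** **Inputs from the protocol**

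- Section 3.6: 12 services, 150 patients per service per 3-month interval, 4 intervals; minimally important reduction in immobilization of 10 points from 100%.
- Section 2.3, Figure 2: 4 services per step, with 3, 2 and 1 intervals under the CCR.
- Section 2.1: in the pilot about 60% of immobilizations avoided, specificity 68%, sensitivity 100%; fractures in under 1% of patients.

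The plan gives no power or sample size for (f). Its total reproduces: 12 × 4 × 150 = 7,200.

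**1. Patients with no device level**

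- CCR phase: (3 + 2 + 1) × 4 × 150 = 3,600. Usual Care: (1 + 2 + 3) × 4 × 150 = 3,600.
- 10% avoided: 0.10 × 3,600 = 360 without a device.
- 60% avoided: 0.60 × 3,600 = 2,160 without a device; 1,440 keep one.

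The collar has its own box on the form, so some immobilized patients may also have no backboard type.

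**2. Immobilization**

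In each device level the proportion immobilized is 100% in both phases. Each contrast is 100% − 100% = 0, and so is their difference, against an overall reduction of 10 to 60 points. No assumption is needed.

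A 'none' level does not help. If Usual Care immobilizes everyone, that level has no Usual Care patients. The device and device-by-treatment design then has 8 columns but rank 7, so the treatment term for 'none' is not estimable. If 2% to 10% of Usual Care patients (72 to 360) went without immobilization, the level would hold 0% immobilized in both phases and again show no effect.

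**3. Comfort (illustration only)**

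Let *r* be the rule-negative share and *a* the share of CCR-phase patients spared, all of them rule-negative. Assume device choice and override are unrelated to comfort, and device choice is unrelated to rule status. The rule-positive share is 1 − *r* among Usual Care patients and (1 − *r*)/(1 − *a*) among CCR-phase patients who are immobilized. The within-device contrast is then *m* × gap, where gap is comfort in rule-positive minus rule-negative patients while immobilized, and

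*m* = (1 − *r*)/(1 − *a*) − (1 − *r*) = (1 − *r*)*a*/(1 − *a*).

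| Scenario | *r* | *a* | *m* | Contrast for an assumed 10-point gap |
|---|---|---|---|---|
| Pilot figures | 0.68 | 0.60 | 0.32 × 0.60/0.40 = 0.48 | 4.8 points |
| 60% avoided, no override | 0.60 | 0.60 | 0.40 × 0.60/0.40 = 0.60 | 6.0 points |
| 10% avoided, pilot specificity | 0.68 | 0.10 | 0.32 × 0.10/0.90 = 0.036 | 0.4 points |
| 10% avoided, no override | 0.10 | 0.10 | 0.90 × 0.10/0.90 = 0.10 | 1.0 point |

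The first row implies that (0.68 − 0.60)/0.68 = 12% of rule-negative patients are immobilized anyway; the third implies (0.68 − 0.10)/0.68 = 85%. A gap of the opposite sign reverses the sign of every contrast.

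**4. The interaction for comfort**

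The true effect among patients who would have received device *d* is *a* × g_d, where g_d is the comfort gain from being spared that device. Assume gains of 0.25 (full board) and 0.083 (KED):

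- True effects: 0.60 × 0.25 = 15 points and 0.60 × 0.083 = 5 points, a difference of 10.
- Planned estimate: 0.48 × (gap for full board − gap for KED), which is 0 for equal gaps. The gains do not appear in it.

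A simulation (12 services, 4 intervals of 150, two devices, gap +0.10, 200 runs) confirms the algebra. With the device known for everyone, the effects were 0.149 and 0.052, a difference of 0.097. With the device as recorded they were 0.047 and 0.048, an absolute difference of 0.002. A separate simulation with three devices and no prognostic selection gave true effects of about 0.18, 0.09 and 0.04, all estimated as about 0. These runs check the algebra under assumed values; they are not evidence about this trial.

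**The case against.** **It is one exploratory line.** Item (f) is one of six subgroup entries and has no allocated power, alpha or decision role. This stands and limits the severity, but the line is pre-specified and cannot answer its stated question.

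**The exact failure would be noticed.** An analyst would see 100% immobilized in every device level and not report the result. That is probably true for immobilization. Comfort and pain are more dangerous, because the model fits and returns a plausible number.

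**The figures are soft.** Much of this stands. The 360 comes from a powering target, so it is a scenario and not a floor: fewer patients would lack a device if fewer immobilizations were avoided. The 12% override is inferred from two pilot figures, not reported. Override is tied to paramedic unease and may track pain, contrary to the illustration. The direction and size of the comfort bias cannot be determined from the protocol. The conclusion does not rest on these figures.

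**The device could mean each service's standard equipment.** The wording does not strictly rule this out, but no text supports it and the form records the device per patient. If that was the intention, it has to be written down.

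**Selection common to all devices cancels in the interaction.** It may, but what remains is zero and not the difference sought.

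**Conclusion.** The concern holds. As written, the treatment interaction for (f) estimates neither the effect of the intervention within a device nor its difference between devices. For immobilization this is exact and follows from the form and the outcome definition. For comfort, pain and the other outcomes it follows because every patient with a device level is immobilized, so the effect of being spared is absent and only differences between selected groups remain.

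At the 10% and 60% scenarios, 360 and about 2,160 of 3,600 CCR-phase patients are left out of the device levels. The comfort figures rest on assumed gaps and gains and show only how a real difference can vanish. The conclusion assumes that the device is read from the patient-level form, as the text implies. The primary and co-primary main analyses, the sample size and the other listed subgroups are not affected by this mechanism.

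**What to change.** Delete (f) from the treatment-interaction subgroups in Section 5.4. Replace it with a descriptive table of device type, with comfort and pain, among immobilized patients, stating that these figures are not intervention effects. If shown by phase, the table displays the same selected comparison, so limiting the comfort and pain columns to Usual Care would be cleaner.

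If the team still wants to study effect modification by device, it could define a service-level attribute from each service's Usual Care period and apply it to all that service's patients. This should be labelled exploratory. It rests on at most 12 services, is confounded with other service characteristics, and is useful only if services differ in the device they mainly use, on which the protocol gives no data.

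The cost is one line in the subgroup list and one table. No new data are needed, and the main analyses and sample size are unchanged.
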